4.11.5 Deaths

A summary of deaths will be provided with the number and percentage of subjects categorised as:

- Related to disease under investigation only
- AE outcome=death only
- AE with outcome of death only (AE start date falling after 30 day follow up period)
- Both related to disease under investigation and with AE outcome = death
- Other deaths

A corresponding listing will also be produced.

4.11.6 Clinical Laboratory, Blood Sample

4.11.6.1 Definitions and Derivations

All local laboratory results collected will be listed (refer to Section 17.1.6, 17.1.7 and Section 10.2 of the CSP for the list of clinical safety laboratory tests to be performed and the SoA for timing and frequency).

Laboratory tests will be grouped according to chemistry, haematology, and coagulation. Listings will be provided for all laboratory results. Laboratory parameters will be assessed at baseline as well as throughout the study.

For chemistry and haematology parameters, laboratory abnormalities with toxicity grades according to the NCI CTCAE version 5.0 will be derived.

Laboratory variables that will be measured are detailed in Table 6.

Table 6: Laboratory Safety Variables

Haematology/Haemostasis (whole blood)	Clinical Chemistry (serum or plasma)	
B-Blasts	S-Albumin	S-C Reactive Protein
B-Blasts/Leukocytes	S-Alkaline Phosphatase (ALP)	S-Factor V Leiden
B-Hematocrit	S-Alanine Aminotransferase (ALT)	S-Gamma Glutamyl Transferase (GGT)
B-Hemoglobin	S-Aspartate Aminotransferase (AST)	S-Glucose
B-Leukocytes (white blood cell count)	S-Bicarbonate	S-Lactate Dehydrogenase (LDH)
B-Lymphocytes (ALC)	S-Direct Bilirubin	S-Magnesium
B-Lymphocytes/Leukocytes	S-Bilirubin (BILI)	S-Phosphate

B-Platelet	S-Indirect Bilirubin	S-Potassium
	S-Calcium	S-Protein
Coagulation	S-Cholesterol	S-Sodium
Activated partial thromboplastin time (APTT)/Prothrombin time (PT)	S-Creatine Kinase (CK or CPK)	S-Triglycerides
Prothrombin international normalized ratio (INR)	S-Chloride	S-Urate
D-dimer (where available at institution)	S-Creatinine	S-Urea Nitrogen
Fibrinogen	S-Creatinine Clearance	
Urinalysis (dipstick)		
U- Erythrocytes/Blood	U-Glucose	U-Protein
U-Ketones		

Abbreviations: B=blood; P=plasma; S=serum; U=urinalysis.

All values will be classified as low (below range), normal (within range), or high (above range) based on local laboratory reference ranges. Results will be converted to standard units. For assessments included in CTCAE version 5.0, the CTCAE grade will be calculated.

Liver Function Parameters

Subjects with elevated post-baseline ALT, AST, or Total Bilirubin will be identified. The number and percentages of these subjects will be tabulated.

4.11.6.2 Presentations

All clinical laboratory results will be listed.

For all continuous laboratory assessments, absolute values, change from baseline will be summarised using descriptive statistics at each time point by dose level/cohort. Box plots of absolute values and change from baseline values for haematology and clinical chemistry parameters will also be presented.

For clinical haematology, clinical chemistry and coagulation endpoints, shift tables from baseline to worst on-treatment value according to reference range classification will be created. CTCAE grade changes from baseline to the maximum on-treatment grade will also be provided. In addition, the number of subjects with ≥ 2 CTCAE grade changes and CTCAE grade changes of 3 or 4 will be summarised by actual dose level/cohort for clinical chemistry and haematology parameters.

Liver Function Parameters

For subjects with “Potential Hy’s law”, the change in the following laboratory parameters from baseline to each post-baseline visit will be summarized: ALT, AST, ALP, GLDH, LDH, GGT, and INR. Individual subject data for these laboratory parameters will be listed as well.

Plots for both maximum post-baseline ALT and AST versus the maximum post-baseline BILI (expressed as multiples of their upper limit of normal [ULN] reference range) will be produced with reference lines at 3 x ULN for ALT and AST and 2 x ULN for total bilirubin.

Liver biochemistry test results over time for subjects with elevated ALT or AST ($\geq 3 \times$ ULN) and elevated bilirubin ($\geq 2 \times$ ULN,) regardless of whether or not these elevations occurred at the same visit, or ALT or AST of $\geq 5 \times$ ULN, will be tabulated and plotted.

4.11.7 Clinical Laboratory, Urinalysis

4.11.7.1 Definitions and Derivations

Urinalysis variables that will be measured are detailed in Table 6.

4.11.7.2 Presentations

Shift tables (“Negative”, “Trace”, “Positive”, “0”, “+”, “++”, “+++”) from baseline to worst on-treatment value will be produced for urinalysis.

4.11.8 Vital Signs

The following vital signs will be assessed and listed:

- Systolic blood pressure (SBP) [mmHg]
- Diastolic blood pressure (DBP) [mmHg]
- Pulse rate (bpm)
- Oral body temperature ($^{\circ}$ C)
- Weight (Kg)
- Height (cm)

Change from baseline in vital signs will be calculated for each post-dose visit.

Descriptive statistics for absolute values and changes from baseline will be presented by dose level.

Absolute values and change from baseline blood pressure and pulse rate will be presented in box plots.

4.11.9 ECGs

The following parameters will be assessed in 12-lead ECGs:

- RR-interval (msec)
- QRS-interval (msec)
- RR-interval (msec)
- QT-interval (msec)

- QTc-interval (msec)
- QT-interval corrected using the Fridericia correction formula (QTcF) (msec)
- Heart rate (beats per minute [bpm])

From these resting 12-lead ECGs values of the QT and RR intervals, the QTcF will be rederived using the following formula:

$$\text{QTcF} = \text{QT}/\text{RR}^{(1/3)} \text{ where RR is in seconds}$$

The ECG will be evaluated by the Investigator as 'Normal', 'Abnormal' or 'Borderline'.

All ECG parameters will be listed by subject including changes from baseline for numeric ECG parameters.

Descriptive statistics for absolute values and changes from baseline will be presented by dose level.

The average of the three individual tracings will be used in summaries and listings. The individual tracings will be also displayed in the data listings.

Box plots of absolute values and change from baseline in ECG parameters over time will be presented.

QTcF outliers (defined as values following IP that are greater than 470 msec or increases from baseline greater than 30 msec) will be summarised using cumulative counts and percentages under the following categories:

- Absolute value > 470 msec
- Absolute value > 480 msec
- Absolute value > 500 msec
- Change from baseline > 30 msec
- Change from baseline > 60 msec
- Absolute value > 470 msec and change from baseline > 30 msec
- Absolute value > 500 msec and change from baseline > 60 msec

The result of echocardiograms at screening and after an abnormal ECG finding (T wave inversion/flattening) will be listed and, if appropriate, presented in a summary table. In addition, the results of all multi-gated acquisition (MUGA) scans to assess left ventricular ejection fraction (LVEF) will be listed. ECG data will be collected by ERT.

4.11.10 Physical Examination

The physical examination will include general appearance of the subject, examination of the skin, eyes, ears, nose, throat, respiratory system, cardiovascular system, abdominal cavity, extremities, musculoskeletal system, lymphatic system, and neurological. Physical Examination results will be listed by subject.

4.11.11 Eastern Cooperative Oncology Group performance status (ECOG PS)

ECOG performance status scores will be assessed at screening and before each dose of AZD4573 according to ECOG criteria as follows:

0 = Fully active, able to carry out all pre-disease activities without restrictions

1 = Restricted in physically strenuous activity but ambulatory and able to carry out work of a light or sedentary nature eg, light housework, office work

2 = Ambulatory and capable of self-care, but unable to carry out any work activities. Up and about more than 50% of waking hours

3 = Capable of only limited self-care, confined to bed or chair more than 50% of waking hours

4 = Completely disabled, cannot carry on self-care, totally confined to bed or chair

5= Death

The ECOG performance status will be listed and summarised as frequency counts by dose level and visit.

4.11.12 B Symptoms

Information on B symptoms (Unintentional Weight Loss within 6 Months, Disease Related Intermittent Fevers > 38 C, Drenching Sweats Especially at Night, Significant Fatigue, Worsening of B-Symptoms compared to baseline, Worsening of B-Symptoms compared to prior visit, comments) will be listed for all subjects and visits.

4.11.13 Tumour lysis syndrome

Tumour lysis syndrome (TLS) is an important identified risk for AZD4573 and an identified risk for acalabrutinib. Subjects will be required to be monitored for TLS for up to 24 hours post dose until they have received at least one AZD4573 dose at the target dose level (ie, for at least the first 3 AZD4573 once-weekly doses), and data will be recorded on the TLS Monitoring forms.

During these TLS assessment periods, blood samples will be collected pre-dose and every 4-6 hours until 24 hours after infusion, for analysis of potassium, calcium, phosphate, uric acid, creatinine and blood urea nitrogen, and subjects will be monitored for clinical signs of TLS (increased creatinine, cardiac arrhythmia, seizure). Laboratory values and clinical signs of TLS occurring during the TLS assessment periods are recorded and evaluated according to Cairo-Bishop criteria under CSP version 1 2, 3 and according to Howard Modification of Cairo-Bishop under CSP version 3, 4, and 5.

If laboratory findings met the Cairo-Bishop criteria for laboratory TLS investigators are instructed to record an AE of laboratory/biochemical TLS. If a clinical sign of TLS is present for the same assessment period as laboratory findings consistent with laboratory TLS, Investigators are instructed to only record an AE of clinical TLS. Thus, there are two data sources contributing to the analysis of TLS: TLS monitoring data and AE data.

All laboratory TLS data will be summarized and presented by dose level under one overall category named “Laboratory TLS confirmed by Cairo-Bishop criteria or Howard Modification of Cairo-Bishop criteria”.

The different TLS laboratory subcategories will be presented under those defined Cairo-Bishop criteria as are considered the most inclusive categories. For example, “Laboratory TLS criteria met: Potassium (\geq 6.0 mmol/L or 6 mg/L)” will be counted under the category “Potassium (\geq 6.0 mmol/L or 6 mg/L) or 25% increase from baseline”.

TLS monitoring data

According to the TLS monitoring schedule in CSP Section 10.2 for Module 1 and Section 19.2 for Module 2 which includes multiple scheduled assessment time points after each infusion of study drug, subjects could have multiple records of “TLS confirmed? = Yes” per infusion. “TLS confirmed? = Yes” means that at least laboratory TLS criteria have been met. TLS monitoring data will be summarised per infusion at episode-level (subjects may have a TLS episode after more than one infusion) and subject-level. A maximum of one TLS episode per infusion per subject will be counted for each infusion. For records of “TLS confirmed? = Yes” and clinical TLS (subjects with data supporting a clinical grading entry for one or more of creatinine abnormality, cardiac arrhythmia, seizure):

- The highest Investigator-assigned clinical Cairo-Bishop grade per infusion and per subject will be summarised separately for creatinine abnormality, cardiac arrhythmia, and seizure.
- The overall Cairo-Bishop grade will be derived based on the highest contributing Investigator-assigned clinical grade (among grades for creatinine abnormality, cardiac arrhythmia, seizure) for each record of clinical TLS; the highest derived overall Cairo-Bishop grade per infusion and per subject will be summarised.
- The number of infusion episodes of TLS per subject will be described categorically and using summary statistics. Time to first onset of TLS (hours from start of infusion to first onset of TLS) will be described using summary statistics according to the earliest timepoint with “TLS confirmed? = Yes” (including subjects without clinical TLS).

Time to first onset of TLS (hours from start of infusion to first onset of TLS) will be described using summary statistics according to the earliest timepoint with “TLS confirmed? = Yes” (including subjects without clinical TLS).

AE data

Investigators can report AEs at any time during the study period, hence reporting of AEs of TLS is not restricted to the 24-hour period after each infusion of study treatment during the ramp-up period. Accordingly, there may be a discrepancy between the number of subjects with an AE of TLS and the number of subjects with a TLS monitoring record of “TLS confirmed? = Yes”. As each CTCAE grade change will be recorded as a separate AE in this study, subjects may have more than one AE record during continuous occurrence of TLS if the severity of TLS changed before resolution. Subject-level summaries will present the maximum CTCAE grade for each subject, event level summaries will present the maximum CTCAE grade for each continuous occurrence. In addition to presentation by MedDRA PT and CTCAE grade within standard AE tables and listings, AEs of TLS will also be presented by MedDRA LLT, as this level of the hierarchy allows distinction between clinical and

laboratory TLS. The number and percentage of subjects with an AE of LLT clinical TLS, laboratory TLS or (unspecified) TLS will be presented by maximum CTCAE grade, and total numbers of AEs. Bar charts showing the number of AEs of TLS and the number and percentage of subjects with AEs of TLS by week since first AZD4573 administration will be presented. Time to first onset of any AE of TLS (days) since first AZD4573 administration will be described using summary statistics.

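### Laboratory TLS is pooled by dose level across two case definitions, with CSP version 3 listed under both, so dose and criterion may be confounded and cannot be separated as planned

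*SAP*

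**What the plan says.** SAP Section 4.11.13 (Tumour lysis syndrome) sets out the following.

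- **Criterion by protocol version.** Laboratory values and clinical signs are "evaluated according to Cairo-Bishop criteria under CSP version 1 2, 3 and according to Howard Modification of Cairo-Bishop under CSP version 3, 4" and 5. Version 3 is in both lists.
- **Pooling.** "All laboratory TLS data will be summarized and presented by dose level under one overall category named" a label that joins the two criteria with an 'or'. No row or column by criterion or by CSP version is planned.
- **Subcategories.** "The different TLS laboratory subcategories will be presented under those defined Cairo-Bishop criteria as are considered the most inclusive categories". The one example given is potassium: a result recorded as meeting the 6.0 mmol/L threshold is counted under a heading that continues "or 25% increase from baseline".
- **Source of the counts.** The monitoring summaries use the recorded TLS-confirmed flag, which "means that at least laboratory TLS criteria have been met". The section does not plan to re-derive that flag from the laboratory values.
- **AE reporting.** "If laboratory findings met the Cairo-Bishop criteria for laboratory TLS investigators are instructed to record an AE of laboratory/biochemical TLS". The Howard modification is not named there, and the clinical grades are called Cairo-Bishop grades throughout.

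Elsewhere, Section 4.2 presents Module 1 summaries by dose level with Parts A and B combined. Section 4.5 ties the opening of Part B and the backfill of Part A to the meeting that declared the RP2D. The Appendix identifies the RP2D as 12 mg. Section 4.11.4 lists TLS as an AESI for AZD4573.

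**The concern.** A rate by dose level can be read only if a case means the same thing at each dose. Here the definition depends on the protocol version in force, and the SAP itself treats one set of headings as wider than the other. Moving threshold results under the wider headings makes the labels uniform but leaves the ascertainment as it was. A subject whose flag was set under the narrower rule, and who had only a 25% rise, has no positive result to move.

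If later protocol versions weigh more heavily on one dose level, part of any difference in TLS between doses could come from the change of criterion. A real dose relation could equally be masked. Safety is the primary objective of Part A, and TLS is described as an important identified risk, so this is a table that readers will use.

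**Working it through.** The SAP states no TLS rate, count or precision target, so there is no figure to reproduce. The check has three parts.

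**1. The version lists.** Cairo-Bishop covers {1, 2, 3} and Howard covers {3, 4, 5}. The intersection is {3}. Either one list is wrong, or the criterion changed during version 3. Nothing in the section says which, or gives a date.

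**2. What relabelling can and cannot do, on the SAP's potassium example.** The wider heading is met at 6.0 mmol/L or at 1.25 × baseline. The baselines below are assumptions.

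| Assumed baseline (mmol/L) | 1.25 × baseline | Meets the wider heading but not the 6.0 threshold |
|---|---|---|
| 3.6 | 4.5 | 4.5 to below 6.0 |
| 4.0 | 5.0 | 5.0 to below 6.0 |
| 4.8 | 6.0 | none |

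A reading in the last column would count in the potassium row if scored on the wider rule and would be absent if scored on the threshold alone. This shows a discordant subcategory reading. It does not show a discordant TLS case, because the SAP does not state how many analytes make a case.

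**3. What an uneven mix could do to the rate by dose.** For one dose level let

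- p = true laboratory TLS rate under Cairo-Bishop, set equal at all doses (no dose effect);
- w = share of that dose's subjects scored by Cairo-Bishop;
- f = share of Cairo-Bishop positives that also meet Howard, with Howard cases taken as a subset.

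Apparent rate = p × [w + (1 − w) × f]. None of p, w or f is in the SAP; all are assumed. For example, with p = 0.30, w = 0.3 and f = 0.5: 0.30 × (0.3 + 0.7 × 0.5) = 0.30 × 0.65 = 19.5%.

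Results at p = 30%:

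| w, lower dose vs 12 mg | f = 0.5 | f = 0.7 | f = 0.9 |
|---|---|---|---|
| 1 vs 0 | 30.0% vs 15.0% (ratio 2.0) | 30.0% vs 21.0% (1.43) | 30.0% vs 27.0% (1.11) |
| 1 vs 0.3 | 30.0% vs 19.5% (1.54) | 30.0% vs 23.7% (1.27) | 30.0% vs 27.9% (1.08) |
| 0.8 vs 0.4 | 27.0% vs 21.0% (1.29) | 28.2% vs 24.6% (1.15) | 29.4% vs 28.2% (1.04) |
| 0.5 vs 0.5 | 22.5% vs 22.5% (1.0) | 25.5% vs 25.5% (1.0) | 28.5% vs 28.5% (1.0) |

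The ratios do not depend on p. The spurious difference is zero if the mix is the same at each dose, or if the criteria agree fully (f = 1).

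**Does w differ by dose?** Part B and the backfill followed the RP2D decision, and Part B subjects are reported at 12 mg with the Part A subjects of that level. Later enrolment, and so later protocol versions, probably weighs more on 12 mg. The SAP gives no cross-table of version by dose.

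**The case against.** The strongest reply is that confounding is inferred. The date of the RP2D decision is redacted, and there are no counts by version. The 12 mg level also contains Part A subjects enrolled before the decision, and Section 4.6.1 speaks of backfill cohorts in the plural, so later subjects at lower doses are not excluded. All of this stands. A reader might infer that TLS incidence by dose is confounded as a matter of fact, or that the RP2D rate is biased low. The SAP supports neither statement: it does not show the mix, and it does not set out the Howard rule or the full case rule. The direction of bias rests on one potassium example and on the remark that the Cairo-Bishop headings are the most inclusive.

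A reader might also infer that the overall category carries the broader label. It does not, since its name gives both criteria. Only the subcategories use Cairo-Bishop wording, and a threshold result does satisfy a heading of threshold or 25% rise. The filing is therefore not false, but the row may be incomplete.

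Other outputs mitigate in part. Section 4.11.6 lists all laboratory results, with summaries and CTCAE shifts that do not depend on the TLS criterion, although the SAP does not say whether the samples on the TLS forms feed them. The AE tables help less, because recording a laboratory TLS event is itself tied to meeting a TLS criterion.

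Finally, the analysis is descriptive, the MTD comes from DLT rates, the RP2D has been declared and enrolment is halted. No decision in the SAP is shown to turn on this table. That limits the consequence. It does not make rows with mixed definitions interpretable.

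**Conclusion.** The point holds in limited form. On the text alone, version 3 is assigned to both criteria without a rule, and two case definitions are pooled by dose level with no split. The subcategory rows can also under-count subjects scored on the narrower rule. The overall rate may be affected too, depending on a case rule that the SAP does not give.

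Confounding of TLS by dose with the criterion is probable from the order of enrolment, but it is not demonstrated. What can be said firmly is that the planned output could not separate the two. The apparent ratios of 1.04 to 2.0 under the uneven mixes above are illustrations on assumed inputs and do not estimate the effect in this trial. The defect lies in the reporting of an AESI. It can be corrected before the analysis and does not threaten the trial's other conclusions.

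**What to change.** 1. Reconcile the version lists in Section 4.11.13: state which criterion applied to version 3 subjects and, if it changed during that version, from what date or amendment.
2. Present laboratory TLS for Module 1 by dose level split by the criterion actually used, with the number of subjects assessed under each as the denominator. Section 4.11.1 already makes the dose-delay derivation depend on CSP version, so such a split appears feasible.
3. As a supportive row, re-derive laboratory TLS for all Module 1 subjects on one common, pre-stated definition, taking the full case rule from the protocol. The pre-dose and serial potassium, calcium, phosphate and uric acid values are already collected.
4. Reconcile the AE recording instruction and the clinical grade labels, which name Cairo-Bishop only, with the statement that Howard was used under later versions.

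The cost is SAP wording, one added derivation and a few more table rows, some with small counts. No new data are needed.

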4.11.14 Other Safety Assessments

4.11.14.1 Presentations

Serum immunoglobulins (IgA, IgM, IgG) will be listed and summarized descriptively.

4.12 Interim Analyses

No interim analyses are planned for the study due to the decision to permanently halt enrolment.

4.13 Determination of Sample Size

Refer to Section 18.2 of the CSP for Module 1 and Section 27.2 of the CSP for Module 2.

4.14 Changes or Clarification to Protocol in the Conduct of the Study or Planned Analysis

CSP version 5.0 is describing the entire statistical analysis originally planned for Module 2, however due to the limited sample size (ie, 3 subjects treated), Module 2 data will not be presented in summary tables and only by-subject listings and figures will be produced.

6 APPENDICES

Module 1 - Part A subjects to be included in Part B analysis

PURPOSE:

This document describes the process for using data from subjects enrolled in Module 1 Part A in analyses for Module 1 Part B. This document describes:

- the process for Cell of Origin (COO) testing, used to identify GCB and non-GCB DLBCL subjects;
- the selection criteria for Part A subjects whose data will be included in the final analysis for Part B;
- the process to document the recycling of Part A subjects data.

PROCESS

1. Cell of Origin (for all part A and part B subjects)

For the purposes of recycling of data from Part A subjects for analysis with Part B subjects data, COO data from local assessment will be used.

2. Definition of Part A subjects that will be included in the Module 1 Part B final analysis

Data from Module 1 Part A subjects will be analysed together with data from Part B subjects if the Part A subjects fulfil all the conditions below:

- Must have received any amount of AZD4573 and acalabrutinib on study;
- Must have been enrolled in the 12 mg (RP2D) dose level cohort;
- Must have a diagnosis of de novo DLBCL, ie:
 - DLBCL NOS (de novo), or
 - High-Grade B cell Lymphoma (NOS), or
 - High-Grade B cell Lymphoma with MYC and BCL2 and/or BCL6 rearrangements;
- Must have measurable disease at baseline (ie be part of the response evaluable set).

3. Documentation of review and confirmation

The Parexel Programming team will programmatically identify Part A subjects whose data can be recycled in Part B for final analysis purposes, based on the criteria described in this document.

Subjects that can be recycled will be marked by population flags in the ADAM and SDTM specifications. TFLs will be generated including the correct individuals (including recycled subjects) in each cohort; a listing of recycled subjects will also be included in the TFLs.

SIGNATURE PAGE

This is a representation of an electronic record that was signed electronically and this page is the manifestation of the electronic signature

Document Name: d8230c00002-sap-ed-5		
Document Title:	Statistical Analysis Plan Edition 5	
Document ID:	Doc ID-004599196	
Version Label:	5.0 CURRENT LATEST APPROVED	
Server Date (dd-MMM-yyyy HH:mm 'UTC'Z)	Signed by	Meaning of Signature
30-Oct-2023 14:53 UTC	PPD 	Content Approval

Notes: (1) Document details as stored in ANGEL, an AstraZeneca document management system.

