4.2 General Presentation Considerations

The following considerations will be applicable to all modules.

Continuous data will be summarised in terms of the mean, standard deviation (Std Dev), median, 25th and 75th percentiles (where appropriate), minimum, maximum and number of observations. If data are available for less than 3 subjects, no summary statistics other than minimum, maximum and number of observations will be presented. For log--transformed data it is more appropriate to present geometric mean (gmean), geometric coefficient of variation (CV), median, minimum and maximum.

Categorical data will be summarised by frequency counts and percentages for each category.

Percentages will be presented to one decimal place. Percentages will not be presented for zero counts. Unless otherwise stated, percentages will be calculated out of the analysis set total and each dose level/cohort.

Confidence intervals (CIs), when presented, will generally be constructed at 2-sided 80% and 95% level. CIs will be presented to one additional place than the original data. When presented, P-values greater than or equal to 0.001, in general, will be presented to three decimal places. P-values less than 0.001 will be presented as “<0.001”.

For continuous data, descriptive summary statistics (mean, median, quartiles, Std Dev, standard error, confidence intervals [CIs]) will be rounded to 1 additional decimal place compared to the original data. Minimum and maximum will be displayed with the same accuracy as the original data.

For categorical data, percentages will be rounded to 1 decimal place. In Module 1, summary tables will be presented by dose level combining Module 1 Part A and Module 1 Part B subjects unless otherwise stated. Data from RP2D-treated Module 1 Part A subjects that meet entry criteria for Module 1 Part B will also be included in Module 1 Part B.

A subgroup analysis will be performed. For the purposes of recycling of data from Module 1 Part A subjects for analysis with Module 1 Part B subject data, cell of origin (COO data) from local assessment will be used. The histology subtype was assigned by local sites, and it was confirmed by central laboratory only for subset of GCB and non-GCB subjects were treated at RP2D (AZD4573 12 mg) and all Module 1 Part B subjects.

Efficacy endpoints may also be summarised by other relevant subgroups (eg, Lymphoma classification, Histology subtype, prior anti-cancer therapies [CAR-T, BiTE and BTKi]).

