Pharmacokinetics (PK)	All dosed subjects with reportable plasma concentration and no important protocol deviations that may impact PK. Subjects will be reported by the actual treatment(s) received and grouped by their assigned target dose level of AZD4573.
Response evaluable	Subjects dosed with AZD4573 or acalabrutinib with measurable disease (longest diameter greater than zero) at baseline.

Analysis Set	Definition
Interim response evaluable	Subjects dosed with AZD4573 or acalabrutinib, or both AZD4573 and acalabrutinib with baseline tumour assessment and have their first post-baseline disease assessment performed or have discontinued study treatment for any reasons before their first post-baseline disease assessment.
Full Analysis Set (ITT)	All subjects who received any amount of AZD4573 and/or acalabrutinib.

Abbreviations: DLT = dose-limiting toxicity; ICF = informed consent form; ITT intention-to-treat;

PK=pharmacokinetics.

Upon database release, protocol deviations and analysis set outputs will be produced and will be sent to AZ for review. Prior to database lock for the primary analysis, an analysis set classification meeting will be arranged to discuss the outputs and to decide which subjects and/or subject data will be excluded from certain analyses. Decisions made regarding the exclusion of subjects and/or subject data from analyses will be made prior to primary analysis lock and will be documented and approved by AZ.

A summary on which analysis set will be used for each outcome variable is provided in [Table 3](#).

Table 3 Summary of outcome variables and analysis sets

Outcome Variable	Analysis Set
Study Population/Demography Data	
Disposition	All Subjects
Demography and baseline characteristics	FAS
Important protocol deviations	FAS
Medical History	FAS
Prior/Concomitant Medication	FAS
Safety data	
Exposure	Safety
Adverse Events	Safety
Laboratory measurements	Safety
Vital Signs/ECG/Physical examination	Safety
ECOG PS	Safety
DLTs	DLT evaluable
Efficacy Data	
CR rate	Response evaluable
TTR	Response evaluable
DoR	Response evaluable

Outcome Variable	Analysis Set
PFS	FAS
OS	FAS
ORR	Response evaluable
Pharmacokinetics	
Pharmacokinetic variables	PK

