4.10.3 Other Efficacy Variables

In Module 1 Part A and Module 2, all efficacy endpoints are exploratory. In Module 1 Part B, all efficacy endpoints other than ORR are secondary.

All listings and summaries will be based on the Response Evaluable Set, except PFS and OS that will be based on the FAS as defined in [Table 3](#).

Tumour response data will be listed and summarised by dose level, if appropriate, using the Lugano Response Criteria for Non-Hodgkin's Lymphoma in Table 17 of the CSP.

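### Part A subjects recycled into Part B must have had both drugs and measurable disease even for PFS and OS, so the recycled Part B survival population is not the FAS and mixes two selection rules

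*SAP*

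**What the plan says.** The appendix in SAP Section 6 sets out "the selection criteria for Part A subjects whose data will be included in the final analysis for Part B". A Part A subject's data are analysed with Part B "if the Part A subjects fulfil all the conditions below". There are four conditions:

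- treatment: "Must have received any amount of AZD4573 and acalabrutinib on study";
- enrolment in the 12 mg (RP2D) cohort;
- a diagnosis in the de novo DLBCL group that the appendix lists;
- disease: "Must have measurable disease at baseline (ie be part of the response evaluable set".

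None of the four is limited to particular endpoints. The selection is programmed and carried by population flags.

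For the analysis sets, Section 4.10.3 states: "All listings and summaries will be based on the Response Evaluable Set, except PFS and OS that will be based on the FAS". Table 3 and Sections 4.10.3.4 and 4.10.3.5 agree. Table 2 in Section 4.5 defines the Full Analysis Set as "All subjects who received any amount of AZD4573 and/or acalabrutinib".

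Section 4.2 gives its own recycling statement: "RP2D-treated Module 1 Part A subjects that meet entry criteria for Module 1 Part B will also be included in Module 1 Part B".

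Table 2 defines the response evaluable set as "Subjects dosed with AZD4573 or acalabrutinib with measurable disease (longest diameter greater than zero) at baseline". Section 4.10.2.1 describes the same set as subjects who received AZD4573 **and** acalabrutinib, with measurable disease.

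**The concern.** The 12 mg and histology conditions match Part A subjects to the dose and disease of Part B, which is what a recycling rule is for. The other two conditions define an analysis set for response. Used as an entry filter for all endpoints, they carry a response-set restriction into PFS and OS, where the plan has chosen the FAS.

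Two otherwise identical 12 mg DLBCL subjects can then be handled differently in the same survival curve, according to the part in which they enrolled. Part B PFS and OS are secondary endpoints and no hypothesis is tested (Section 4.10.1), so the descriptive estimates are the result and it should be clear who is counted in them. Having Section 4.2 and the appendix select the same pool in different words also leaves room for two versions of the recycled cohort, which reaches the primary endpoint, ORR, as well.

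**Working it through.** The plan states no figure to reproduce. The check is a comparison of set definitions, followed by an illustrative size.

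**1. Who enters Part B PFS and OS**

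- Enrolled in Part B (Table 2, FAS): AZD4573 *or* acalabrutinib, any amount.
- Recycled from Part A (appendix): AZD4573 *and* acalabrutinib, *and* measurable disease, *and* 12 mg cohort, *and* de novo DLBCL.

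For a 12 mg de novo DLBCL subject:

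| Subject | Enrolled in Part B | Enrolled in Part A |
|---|---|---|
| Both drugs, measurable disease | in PFS/OS | in PFS/OS |
| One drug only, measurable disease | in PFS/OS | left out |
| Both drugs, no measurable disease | in PFS/OS | left out |

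The second and third rows are the inconsistency.

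**2. Does the plan expect such subjects in PFS?** Yes. Section 4.10.3.4 and Table 4 deal with subjects who have no baseline tumour assessment: an early death is an event, otherwise the subject is censored at Day 1. A subject without a baseline assessment could hardly pass a condition of measurable disease at baseline. The PFS rules thus provide for subjects whom the recycling filter would remove.

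**3. Section 4.2 against the appendix.** Section 4.2 requires treatment at the RP2D and the Part B entry criteria. It mentions neither both drugs nor response evaluability. The appendix requires those two and does not mention the Part B entry criteria. The two rules coincide only if the entry criteria, which stand in the protocol, happen to imply the same subjects.

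**4. The set the appendix points to.** Table 2 uses *or* and Section 4.10.2.1 uses *and*. Under Section 4.10.2.1, the appendix conditions agree with the ORR population. Under Table 2, a Part B subject who had only one drug counts for ORR while the Part A counterpart does not.

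**5. Which outputs are touched.** Section 4.2 makes the default Module 1 table one by dose level with Parts A and B combined. A Part A 12 mg subject who fails recycling is still in the 12 mg FAS there. Only outputs that show Part B with recycled subjects are affected.

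**6. Illustrative size.** Let n be the pooled subjects shown and S the landmark rate, with follow-up complete to the landmark. Adding one omitted early failure changes the rate from S to nS/(n+1), so the omission had raised it by

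S − nS/(n+1) = S/(n+1).

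Assumed ranges, not from the SAP: n = 30 to 40, S = 30 to 60%.

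- Low end: 0.30/41 = 0.0073, or 0.7 points.
- High end: 0.60/31 = 0.0194, or 1.9 points.

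If the omitted subject was instead event-free at the landmark, the omission lowers the rate by (1 − S)/(n+1). The direction therefore depends on who is left out.

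**The case against.** Four points can be made for the plan as written.

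- **The main tables are safe.** The default layout by dose level keeps every treated 12 mg subject in PFS and OS. This stands and limits the point to outputs showing Part B with recycled subjects.
- **The filter may exclude nobody.** If the Part B entry criteria require measurable disease, that condition only matches recycled to enrolled subjects. Section 3.3.2 takes PK for AZD4573 and acalabrutinib from Cycle 1 Day 1 of Week 1, which suggests that both normally start together, so few subjects would have had only one. This also stands: the number affected may be zero.
- **The appendix is the operational text.** It says that programmers will use its criteria, and Table 1 and Section 4.7 refer to the recycling document. This makes it likely that the appendix would be followed. It does not remove the different wording in Section 4.2, and following the appendix is what produces the mismatch with the FAS.
- **The analysis is descriptive and PFS and OS are secondary.** True, and it bears on weight rather than on correctness.

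A reader might infer that the Part B survival curves are biased upwards. The document does not support that. The both-drugs condition could remove early failures, but nothing shows that such subjects exist. Measurable disease is a baseline trait, and excluding on it has no known direction. A reader might also take each lost early failure to move a landmark rate by 1/n (2.5 to 3.3 points for n = 40 to 30). The shift is S/(n+1), and 1/n is only roughly its ceiling as S approaches 100%.

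**Conclusion.** The inconsistency holds on the text. One recycling filter, with two response-set conditions, applies to every endpoint of the Part B final analysis, while Part B-enrolled subjects enter PFS and OS under the wider FAS definition. Where Part B is shown with recycled subjects, the PFS and OS population is not an FAS. Section 4.2 states a different recycling rule, and the response evaluable set is defined in two ways.

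The size is unknown. The SAP gives no count of Part A 12 mg subjects who fail either condition. The range of 0.7 to 1.9 points per omitted early failure rests wholly on the assumed n and S and on complete follow-up to the landmark. This is a defect in set definition that should be corrected; it is not a demonstrated bias.

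**What to change.** 1. In the appendix, separate eligibility for recycling from membership of an analysis set. Eligibility: 12 mg cohort, de novo DLBCL as listed there, and the Part B entry criteria.
2. Then apply the analysis sets identically to recycled and Part B-enrolled subjects: the FAS definition for PFS and OS, and the response evaluable definition for ORR, CR rate, TTR and DoR. The both-drugs and response-evaluable conditions cease to be recycling filters for PFS and OS.
3. Have Section 4.2 cross-refer to this single rule. Keep the match to the Part B entry criteria: replacing it with the present appendix conditions could admit Part A subjects who do not resemble the Part B population.
4. Reconcile the response evaluable definition between Table 2 and Section 4.10.2.1 (*or* against *and*).

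The cost is SAP wording and one further population flag. No new data are needed.
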